6.12.2. Laboratory Data

For Part A and Part B, the following analysis will be undertaken separately. Descriptive statistics of the observed values and change from baseline (continuous data) will be presented by treatment and visit for each hematology (including coagulation), urinalysis, and serum chemistry (including fasting lipid panel and fasting glucose) parameter. Each measurement (continuous data) will be classed as below, within, or above normal range, based on ranges supplied by the laboratory used. Shift tables in relation to the normal range from baseline to each follow-up visit will be presented.

A listing of any clinically significant laboratory measurements recorded throughout the study will be presented.

All laboratory data, will be listed for example:

- Serology testing: hepatitis B, hepatitis C, and HIV
- Urine drug, alcohol, and cotinine screen tests.
- Serum pregnancy tests (all female subjects)
- FSH tests (female subjects claiming post-menopausal status)

6.12.3. Vital Signs

For Part A and Part B, the following will be presented separately. Descriptive statistics for observed values and changes from baseline to post dose assessments in the following vital signs will be presented by treatment at each visit:

- Systolic blood pressure (mmHg)
- Diastolic blood pressure (mmHg)
- Pulse rate (bpm)
- Respiration rate (breath/min)
- Body temperature (degrees Celsius)
- Pulse oximetry (%)

All vital sign data will be listed.

6.12.4. Pulmonary Function Test

For Part A and Part B, the following will be presented separately. Descriptive statistics for observed values and changes from baseline to post dose assessments in the following pulmonary function tests (FEV1 and FVC; best of 3 reproducible maneuvers) will be tabulated by treatment. All pulmonary function test data will be listed.

The details of exploratory analysis are shown in Section 6.11. All statistical output will be listed and figures produced for the scatter plots.

6.12.5. Electrocardiogram Data

For Part A and Part B, the following will be presented separately. Descriptive statistics for observed values and changes from baseline to post dose assessments in the following ECG quantitative variables will be tabulated by treatment at each visit:

- Heart rate (bpm)
- PR interval (msec)
- RR interval (msec)
- QRS duration (msec)
- QT interval (msec)
- QTc interval (msec)
- QTc interval (msec) [Bazett's formula QTcB]
- QTc interval (msec) [Fridericia's formula QTcF]

• Note: Bazett's formula is QTcB=QT/ $\sqrt{(RR)}$, Fredericia's formula is QTcF=QT/ $\sqrt[3]{(RR)}$

Shift tables in relation to the overall interpretation (Normal, Abnormal Not Clinically Significant [NCS], and Abnormal Clinically Significant [CS]) from baseline to each follow-up visit will be presented.

All ECG data, including details of any abnormalities, will be listed.

6.12.6. Physical Examination

For Part A and Part B, all data, including details of clinically significant findings, will be listed.

6.12.7. Other Safety Analysis

For Part A and Part B, chest X-ray details will be listed only. Purified protein derivative (PPD) skin test and thyroid-stimulating hormone (TSH) tests will be listed only with serology testing.

If available buffy coat will be tabulated by treatment and listed, including change from baseline.

7. SAFETY REVIEW COMMITTEE

The bioanalytical laboratory and pharmacokineticist will be unblinded to allow for analysis and presentation for the assessment by the safety review committee between cohorts. The data presented to the safety review committee will not contain subject-level identifiers in order to maintain the blind of the participants of the safety review unless there is a study emergency. Only the bioanalytical lab and pharmacokineticist will be unblinded for data preparation.

Interim pharmacokinetic analysis will include:

Blinded Concentration vs. Time Table (summary statistics) stratified by Cohort (SAD) and Cohort and Day (MAD)

Mean Concentration vs. Time Profile comparing doses (SAD and MAD) and Days 1 and 7 (MAD)

Mean concentration vs. Time profiles comparing Gender within each Cohort

Blinded PK parameters (summary statistics) stratified by Cohort (SAD) and Cohort and Day (MAD).

Blinded PK parameters (summary statistics) stratified by Cohort and Gender (SAD) and Cohort, Day, and Gender (MAD).

Scatterplots for Part A (SAD):

 $C_{max},\,AUC_{0\text{-}24},\,AUC_{last},\,AUC_{inf},\,and\,\,T_{1/2}$ vs. baseline FVC

 $C_{max},\,AUC_{0\text{-}24},\,AUC_{last},\,AUC_{inf},\,and\,\,T_{1\!\!/_{\! 2}}\,vs.$ baseline FEV1

Scatterplots for Part B (MAD):

C_{max}, AUC₀₋₂₄, and T_{1/2} vs. baseline FVC

C_{max}, AUC₀₋₂₄, and T_{1/2} vs. baseline FEV1

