5. RANDOMIZATION

Subjects will be randomized into one dose cohort and receive either PK10571 or placebo. Within each cohort, 6 subjects will receive active drug and 2 subjects will receive placebo.

For both the SAD and MAD parts each cohort, randomization will occur in 2 blocks as follows: In the first block, 2 subjects (sentinel subjects) will be randomized 1:1 to receive PK10571 or placebo; in the second block, 6 subjects will be randomized 5 PK10571: 1 placebo. If PK10571 is well-tolerated in the sentinel subjects, the remainder of the cohort (n = 6) will be randomized. There will be a minimum of 48 hours between dosing of the 2 sentinel subjects and the remainder of the cohort.

Gender distribution will be based on sequential screening of volunteers who meet entry criteria, with a minimum of 4 females per cohort, in order to ensure 2 females per active dose group. Subjects will be assigned numbers in an ascending order, based on successful completion of the screening process. Each subject will participate in only one cohort.

Subjects who withdraw from the study may be replaced at the discretion of the Principal Investigator and Sponsor.

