6.2.3. Baseline

Baseline is defined as the last non-missing value (either scheduled, unscheduled or repeat) before the subject receives the first dose of study drug in both Part A and Part B.

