V _z /F	Apparent volume of distribution in the terminal phase (Day 7 only), presented to 3 significant figures	
	Vz/F will be presented with and without weight-adjustment. Weight adjustment will be calculated as Vz/F x 70/body weight in kg.	
Rac	Accumulation ratio during multiple dosing; presented to 3 significant figures and calculated as:	
	RAC=AUC ₀₋₂₄ Day 7/AUC ₀₋₂₄ Day 1	
$\lambda_z \left(K_{el} , \right. \\ Lambda z)$	Apparent terminal elimination rate constant calculated by linear regression of the terminal linear portion of the log concentration versus time curve (Day 7 only), presented to 3 significant figures	
Т½	The observed terminal elimination half-life, presented to 3 significant figures and calculated as:	
	$T_{1/2} = \ln(2)/\lambda_z$ (Day 7 only)	

No value for λ_z and other λ_z -related parameters (AUC_{inf}, $T_{1/2}$, etc.) will be reported if λ_z cannot be estimated.

PK concentration data will be summarized by study part, treatment, and day (for MAD study part) at each nominal sample time. PK parameter data will be summarized by study part, treatment, and day (for MAD study part). PK parameter data will also be stratified by sex and for males and females combined. PK parameter tables will include columns for baseline BMI, FEV1, and FVC.

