6.3. Conventions

All clinical summaries, figures and statistical analyses will be generated using SAS (Version 9.4 or higher)².

Summaries of the clinical data will be presented by treatment group. In addition, disposition, demographic, and baseline summaries will include an overall column that consists of all subjects.

PK data listings, summaries, figures, and statistical analyses will be generated using Phoenix[™] WinNonlin[®] (Version 6.3 or higher) or SAS (Version 9.4 or higher).

Treatment group labels will be displayed as follows:

Cohort	Test Formulation
1	Placebo
1	PK10571 FPD
2.	Placebo
2	PK10571 FPD
3	Placebo
3	PK10571 FPD
4	Placebo
4	PK 10571 FPD
5	Placebo
5	PK10571 up to FPD

Cohort	Test Formulation
1	Placebo
1	PK10571 initial dose
2	Placebo
2	PK10571 mid dose*
2	Placebo
3	PK10571 high dose*

Note: The dosing regimen will be either once daily (QD), twice daily (BID), or three times daily (TID) for 7 consecutive days. For TID dosing, each daily administration will be separated by 6 hours. Placebos will be grouped together within summary tables.

*Alternately, Cohort 2 and 3 will receive a lower dose, depending upon safety and pharmacokinetic data from Cohort 1 or 2, respectively.

The initial (lower) dose for Part B will be determined after review of the safety and pharmacokinetic data from Part A.

The data from the lower dose cohort will be analyzed before deciding whether to proceed with the higher dose cohorts.

Listings will be sorted in the following order: treatment, subject, parameter, and visit unless otherwise stated. All data will be listed.

For clinical data, continuous variables will be summarized by the number of non-missing observations, mean, median, standard deviation, and minimum and maximum.

PK data (concentration-time data and PK parameters) will be summarized by (n), mean, standard deviation (SD), median, minimum (min), maximum (max), and coefficient of variation (CV%). In addition, the geometric mean and geometric CV% will be reported for all PK parameters except T_{max}. T_{max} will be presented as median, minimum, and maximum.

Baseline values for FEV1, FVC, and BMI, defined as the values obtained prior to and closest in time to the first dose, will also be summarized by the number of non-missing observations (n), mean, standard deviation (SD), median, minimum (min), maximum (max), and coefficient of variation (CV%).

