6.3.1. Decimal Places

Decimal places for derived data described in section 6.2.10 will be determined by the scale of measurement unless otherwise stated. No decimal places will be displayed if the smallest calculated value is ≥ 100 ; 1 decimal place will be displayed when the smallest value is within the interval (10, 100), with 10 being inclusive; 2 decimal places will be displayed when the smallest value is within (1, 10), with 1 being inclusive; and so on for even smaller scales of measurement.

Derived data where it is known in advance the result will be an integer (for example, day, month, year and number of days) will be presented with zero decimal places.

Means, medians and percentiles will be displayed to one more decimal place than the data, dispersion statistics (e.g., standard deviation) will have two more decimal places, and the minimum and maximum will be displayed to the same number of decimal places as reported in the raw data. Percentages will be displayed with one decimal place.

For PK data, individual concentrations will be reported to 3 significant figures and individual PK parameters will be reported to the precision as stated in Section 6.2.10. For summary statistics, n will be reported as a whole number; mean, standard deviation, median, minimum, maximum, and geometric mean will be reported to the same precision as for individual data. CV% and geometric CV% will be reported to 2 decimal places; p-values will be reported to 4 decimal places. Percent ratios of the geometric least squares means and associated 95% confidence intervals will be reported to 2 decimal places.

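### The interim scatterplots against baseline FVC and FEV1 in SAP 7 could let a blinded Safety Review Committee member infer allocation, although they carry no subject identifiers

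*SAP*

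**What the plan says.** SAP 7 states its aim for the committee: the data "will not contain subject-level identifiers in order to maintain the blind of the participants of the safety review", except in a study emergency. Only the bioanalytical laboratory and the pharmacokineticist are unblinded to prepare the data.

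Most of the interim list is aggregate: concentration summaries, mean profiles and "Blinded PK parameters (summary statistics) stratified by Cohort (SAD) and Cohort and Day (MAD"), with further versions by gender. The exception is a set of scatterplots. In Part A, Cmax, three AUC measures and half-life are each plotted "vs. baseline FVC" and again against baseline FEV1. In Part B, Cmax, AUC0-24 and half-life are plotted in the same two ways. SAP 7 sets no axis format, masking or restriction on who sees them.

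Several other places bear on what these plots reveal:

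- SAP 6.1.2 limits the PK population to subjects who received active drug and had a quantifiable postdose concentration.
- SAP 6.2.3: "Baseline is defined as the last non-missing value (either scheduled, unscheduled or repeat) before the subject receives the first dose of study drug".
- Protocol 5.10.2 schedules spirometry at screening and check-in for every subject.
- SAP 5 gives two active-to-placebo blocks per cohort: two sentinels 1:1, then "in the second block, 6 subjects will be randomized 5 PK10571: 1 placebo". That makes six active and two placebo.
- Protocol 3.3 puts the Principal Investigator or designee on the committee. Protocol 5.2 requires the Principal Investigator and all clinical staff who assess subjects to stay blinded.

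**The concern.** The stated purpose is to keep committee members blind, and removing subject numbers does not fully achieve it. A baseline FVC is a number the site has already recorded against a named subject. A plot of FVC for active subjects only, shown to someone with access to all eight FVC values, works as a quasi-identifier: a value with a point belongs to an active subject, and a value without one points to placebo.

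Two judgements are exposed. Protocol 3.5 applies the escalation stopping rules only to events that the committee considers drug-related. Protocol 6 has the Investigator or a Sub-Investigator assign relatedness for each adverse event. In Part A the escalation review waits for Day 11 safety data, and Day 11 is the last visit, so the exposure there is mainly to the committee's own relatedness judgement. In Part B, Protocol 3.3 requires safety data through Day 14 before Cohort 2 is dosed, while adverse events are collected to Day 35. Events assessed between a review and Day 35 are therefore also exposed. This can affect at most Cohorts 1 and 2, which is 2 × 8 = 16 of up to 24 subjects.

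**Working it through.** **Chain from plot to allocation**

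1. Each cohort has 1 + 5 = 6 active and 1 + 1 = 2 placebo subjects (SAP 5). Only the six active subjects can have points (SAP 6.1.2).
2. The x-value is the last pre-dose reading (SAP 6.2.3), which the site holds for all eight subjects (Protocol 5.10.2).
3. A subject's point has the same PK value on the FVC plot and the FEV1 plot, so the two can be paired and read as one (FVC, FEV1) position.
4. If six points appear for a cohort, the two subjects without a point are the placebo subjects.

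**Size.** The plan gives no figure to reproduce, and the documents give neither spirometry spread nor plot resolution. The inputs below are assumptions.

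- FVC: women 3.5 ± 0.5 L, men 4.9 ± 0.7 L. FEV1/FVC: 0.80 ± 0.05.
- Cohort mix: four women and four men (4F/4M), or eight women (8F). The planned minimum is four women per cohort, so these are the two extremes.
- Reading tolerance t: 0.05, 0.10 or 0.20 L.
- The points of the cohort in question can be told apart from other cohorts. SAP 6.11 uses a different symbol for each cohort; SAP 7 does not repeat this.

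A placebo subject is shown to have no point if no active subject in the cohort satisfies both |ΔFVC| ≤ t and |ΔFEV1| ≤ t. For the FVC plot alone, only the first condition is used. The share of simulated cohorts (100,000 per scenario) in which this holds for both placebo subjects is:

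| Plots used | Mix | t = 0.05 L | 0.10 L | 0.20 L |
|---|---|---|---|---|
| FVC and FEV1 | 4F/4M | 95% | 83% | 51% |
| FVC and FEV1 | 8F | 90% | 66% | 24% |
| FVC only | 4F/4M | 71% | 51% | 25% |
| FVC only | 8F | 51% | 26% | 8% |

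A separate run with a different random seed agreed to within about one percentage point.

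Sensitivity: with all SDs changed by ±20%, both plots and t = 0.20 L, the share is 43 to 58% (4F/4M) and 14 to 35% (8F).

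The result also depends on the criterion. A different check asked whether only one of the 2 × 6 = 12 allocations allowed by the two blocks survives. It assumed mean female FVC 3.7 L, SD 0.4 to 0.8 L, a male-female gap of 0.8 to 1.2 L and FEV1/FVC 0.82 ± 0.05. At 0.2 L reading resolution, with four women and four men, it gave 55 to 71% for FVC alone and 86 to 92% for both plots. The criterion in the table is the stricter one.

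**A second route that needs no spirometry.** SAP 7 also supplies PK summaries by gender. In a 4F/4M cohort, if sex is independent of randomisation block, both placebo subjects share a sex with probability

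[C(4,2) + C(4,2)] / C(8,2) = (6 + 6)/28 = 3/7 ≈ 43%.

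The active n by sex is then 2 and 4, and the 4 shows every subject of that sex to be active. Protocol 5.1 also mentions randomising in blocks of four by gender. If that scheme were used, the 3/7 would not apply as calculated.

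**The case against.** - **Nothing is literally breached.** An unlabelled point is not a subject identifier. A reader might infer that SAP 7 contradicts itself, but the documents do not support that: the promise is about identifiers, and the plots carry none. The gap is between the purpose of the promise and the listed outputs.
- **Someone would have to decode the plots on purpose.** Points must be compared with site records. Protocol 5.2.3 treats breaking the blind outside an emergency as a protocol violation, and Protocol 5.2 makes the Principal Investigator responsible for the blind. This stands: the percentages describe a determined decoder, not ordinary review. A missing point can also be an active subject who was not evaluable (Protocol 8.1) or had no quantifiable concentration (SAP 6.1.2).
- **The tables may not carry the same risk.** SAP 6.2.11 says "PK parameter tables will include columns for baseline BMI, FEV1, and FVC", and SAP 6.3 says those baseline values "will also be summarized by the number of non-missing observations (n), mean, standard deviation (SD), median, minimum (min), maximum (max"). A reader might infer that the interim tables also disclose allocation through these columns. That rests on silence: SAP 7 describes its own tables as blinded summary statistics, and nothing carries the SAP 6.2.11 layout into them. It justifies a clarifying sentence only.
- **No inference is affected.** Safety analyses are descriptive, and no test, interval or sample size changes. This also stands. What is at risk is the blinding of relatedness judgements.
- **The committee has reason to look at exposure.** Cmax and AUC are escalation factors under Protocol 3.4. They remain available as summaries; lung function against exposure is not on that list.

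**Conclusion.** The point holds as a gap in blinding protection, and it should be fixed. Followed as written, SAP 7 gives a committee that includes a blinded investigator or designee individual points for active subjects only, on an axis that person can match to site records.

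Under the assumed spirometry, using both plots, both placebo subjects could be identified as having no point in roughly half to nearly all 4F/4M cohorts, and in a quarter to nine-tenths of 8F cohorts, depending on how finely the plots can be read. With FVC alone at a coarse reading the share falls to 8% in 8F cohorts. These figures rest on assumed spread, resolution and deliberate matching, so confidence in the size is moderate. The route itself follows from the text.

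A reader might go further and conclude that the investigator will be unblinded or that relatedness calls will be biased. The documents show only that the opportunity exists.

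**What to change.** In SAP 7:

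1. Delete the FVC and FEV1 scatterplots (Parts A and B) from the interim package, or restrict them before database lock to unblinded staff who do not assess subjects, such as the pharmacokineticist. Keep them in the final analysis under SAP 6.11.
2. As a precaution, state that interim PK tables omit the baseline BMI, FEV1 and FVC columns of SAP 6.2.11.
3. Suppress n, minimum and maximum in interim tables and profiles split by sex, or restrict those outputs to unblinded staff, because the active n by sex can itself reveal allocation.

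The cost is a short change of wording in SAP 7 and small changes to interim table shells. Blinded members lose an exploratory look at lung function against exposure and some detail by sex. Neither is among the escalation factors in Protocol 3.4, and the cohort-level Cmax and AUC summaries remain.

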8. CHANGES TO PLANNED PROTOCOL ANALYSIS

No changes planned to protocol analysis.

APPENDIX 1: LIST OF TABLES, FIGURES AND LISTINGS

The following table includes details of the tables, figures and listings to be included within each section of the electronic common technical document (eCTD). The eCTD section is shown in bold. The following validation methods maybe used:

- Independent programming of numbers and manual review of format (IP)
- Independent programming by statistician of numbers and manual review of format (Stat IP)
- Manual review (MR)
- Code review (CR)

Note: Table, Figure, and Listing numbers/titles are subject to change after final analysis.

Table Number	Table Title	Validation Method	Shell Number (if repeat)
Items in bold are	not table titles but references to the section headings	within eCTD.	
14.1	Demographics Data		
14.1.1	Disposition		
14.1.1.1a	Subject Disposition, (SAD) – Randomized	IP	
	Subjects		
14.1.1.1b	Subject Disposition, (MAD) – Randomized	IP	
	Subjects		
14.1.2	Demographics		
14.1.2.1a	Demographics (SAD) - Safety Population	IP	
14.1.2.1b	Demographics (MAD) - Safety Population	IP	
14.1.3	Baseline Characteristics		
14.2	Efficacy Data		
	Not Applicable		
14.3	Safety Data		
14.3.1	Displays of Adverse Events		
14.3.1.1a	Adverse Events, Overall Summary of Treatment-	IP	
	Emergent Adverse Events (TEAEs) (SAD) –		
	Safety Population		
14.3.1.1b	Adverse Events, Overall Summary of Treatment-	IP	
	Emergent Adverse Events (TEAEs) (MAD) –		
	Safety Population		

Table Number	Table Title	Validation Method	Shell Number (if repeat)
14.3.1.2a	Adverse Events, Treatment Emergent Adverse Events by Primary System Organ Class and Preferred Term (SAD) – Safety Population	IP	
14.3.1.2b	Adverse Events, Treatment Emergent Adverse Events by Primary System Organ Class and Preferred Term (MAD) – Safety Population	IP	
14.3.1.3a	Adverse Events, Treatment Related, Treatment Emergent Adverse Events by Primary System Organ Class and Preferred Term (SAD) – Safety Population	IP	
14.3.1.3b	Adverse Events, Treatment Related, Treatment Emergent Adverse Events by Primary System Organ Class and Preferred Term (MAD) – Safety Population	IP	
14.3.1.4a	Adverse Events, Serious Treatment Emergent Adverse Events by Primary System Organ Class and Preferred Term (SAD) – Safety Population	IP	
14.3.1.3.4b	Adverse Events, Serious Treatment Emergent Adverse Events by Primary System Organ Class and Preferred Term (MAD) – Safety Population	IP	
14.3.1.5a	Adverse Events, Treatment Emergent Adverse Events by Primary System Organ Class, Preferred Term and Maximum Severity (SAD) – Safety Population	IP	
14.3.1.5b	Adverse Events, Treatment Emergent Adverse Events by Primary System Organ Class, Preferred Term and Maximum Severity (MAD) – Safety Population	IP	
14.3.1.6a	Adverse Events, Treatment Related Treatment Emergent Adverse Events by Primary System Organ Class Preferred Term and Maximum Severity (SAD) – Safety Population	IP	
14.3.1.6b	Adverse Events, Treatment Related Treatment Emergent Adverse Events by Primary System	IP	

Table Number	Table Title	Validation Method	Shell Number (if repeat)
	Organ Class Preferred Term and Maximum		
	Severity (MAD) – Safety Population		
14.3.1.7a	Adverse Events, Treatment Emergent Adverse Events by Primary System Organ Class and Relationship to Study Drug (SAD) - Safety Population	IP	
14.3.1.7b	Adverse Events, Treatment Emergent Adverse Events by Primary System Organ Class and Relationship to Study Drug (MAD) - Safety Population	IP	
14.3.1.8	Adverse Events, Treatment Emergent Adverse Events by Primary System Organ Class by Study Part and Study Drug -Safety Population	IP	
14.3.2	Listings of Deaths, Other Serious and		
	Significant Adverse Events		
14.3.2.1	SAE Listing – Safety Population	IP	
14.3.2.2	Deaths, Listing – Safety Population	IP	
14.3.2.3	Listing of Early Termination –Safety Population	IP	
14.3.3	Narratives of Deaths, Other Serious and		
	Certain Other Significant Adverse Events		
	Not Applicable		
14.3.4	Abnormal Laboratory Values		
14.3.4.1	Laboratory, Listing of Clinically Significant Values – Safety Population	IP	
14.3.5	Extent of Exposure, Dosage Information, and Compliance		
14.3.5.1b	Extent of Exposure – Safety Population	IP	
14.3.6	Vital Signs and Physical Examination		
14.3.6.1a	Vital Signs, Change from Baseline (SAD) – Safety Population	IP	
14.3.6.1b	Vital Signs, Change from Baseline (MAD) – Safety Population	IP	
14.3.7	Other Safety		
14.3.7.1a	Hematology Data, Change from Baseline (SAD) – Safety Population	IP	

Table Number	Table Title	Validation Method	Shell Number (if repeat)
14.3.7.1b	Hematology Data, Change from Baseline (MAD) – Safety Population	IP	
14.3.7.2a	Hematology Data, Normal Range Shifts (SAD)– Safety Population	IP	
14.3.7.2b	Hematology Data, Normal Range Shifts (MAD) – Safety Population	IP	
14.3.7.3a	Serum Chemistry Data, Change from Baseline (SAD) – Safety Population	IP	
14.3.7.3b	Serum Chemistry Data, Change from Baseline (MAD) – Safety Population	IP	
14.3.7.4a	Serum Chemistry Data, Normal Range Shifts (SAD) – Safety Population	IP	
14.3.7.4b	Serum Chemistry Data, Normal Range Shifts (MAD)– Safety Population	IP	
14.3.7.5a	Urinalysis Data, Change from Baseline (SAD)— Safety Population	IP	
14.3.7.5b	Urinalysis Data, Change from Baseline (MAD)– Safety Population	IP	
14.3.7.6a	Urinalysis Data, Normal Range Shifts (SAD)– Safety Population	IP	
14.3.7.6b	Urinalysis Data, Normal Range Shifts (MAD) – Safety Population	IP	
14.3.7.7a	Platelet Aggregation Data, Change from Baseline (SAD) – Safety Population	IP	
14.3.7.7b	Platelet Aggregation Data, Change from Baseline (MAD) – Safety Population	IP	
14.3.7.8a	Platelet Aggregation Data, Normal Range Shifts (SAD) – Safety Population	IP	
14.3.7.8b	Platelet Aggregation Data, Normal Range Shifts (MAD) – Safety Population	IP	
14.3.7.9a	ECG Data, Change from Baseline (SAD) – Safety Population		
14.3.7.9b	ECG Data, Change from Baseline (MAD) – Safety Population	IP	

Table Number	Table Title	Validation Method	Shell Number (if repeat)
14.3.7.10a	ECG Data, Overall Interpretation (SAD) – Safety Population	IP	
14.3.7.10b	ECG Data, Overall Interpretation (MAD)– Safety Population	IP	
14.3.7.11a	Pulmonary Function, Change from Baseline (SAD) -Safety Population	IP	
14.3.7.11b	Pulmonary Function, Change from Baseline (MAD) -Safety Population	IP	
14.3.8	Concomitant Medication		
	Not Applicable		
14.4	PK Tables		
14.4.1	Descriptive Statistics for Concentration-Time Data of PK10571 in Plasma after Single Dose Administrations of FPD (Cohort 1), FPD (Cohort 2), FPD (Cohort 3), FPD (Cohort 4), and FPD (Cohort 5) Part A		
14.4.2	Descriptive Statistics for Concentration-Time Data of PK10571 in Plasma after Single Dose Administrations of FPD (Cohort 1), FPD (Cohort 2), FPD (Cohort 3), FPD (Cohort 4), and FPD (Cohort 5) Part A - Stratified by Sex		
14.4.3	Descriptive Statistics for Concentration-Time Data of PK10571 in Plasma after Administration of xx mg FPD (Cohort 1), xx mg FPD (Cohort 2), and xx mg FPD (Cohort 3) on Day 1 Part B		
14.4.4	Descriptive Statistics for Concentration-Time Data of PK10571 in Plasma after Administration of xx mg FPD (Cohort 1), xx mg FPD (Cohort 2), and xx mg FPD (Cohort 3) on Day 1 Part B – Stratified by Sex		

Table Number	Table Title	Validation Method	Shell Number (if repeat)
14.4.5	Descriptive Statistics for Concentration-Time Data of PK10571 in Plasma after Administration of xx mg FPD (Cohort 1), xx mg FPD (Cohort 2), and xx mg FPD (Cohort 3) on Day 7 Part B		repeate
14.4.6	Descriptive Statistics for Concentration-Time Data of PK10571 in Plasma after Administration of xx mg FPD (Cohort 1), xx mg FPD (Cohort 2), and xx mg FPD (Cohort 3) on Day 7 Part B – Stratified by Sex		
14.4.7	Descriptive Statistics for Trough Concentration- Time Data of PK10571 in Plasma after Administration of xx mg FPD (Cohort 1), xx mg FPD (Cohort 2), and xx mg FPD (Cohort 3) on Part B		
14.4.8	Descriptive Statistics for Trough Concentration- Time Data of PK10571 in Plasma after Administration of xx mg FPD (Cohort 1), xx mg FPD (Cohort 2), and xx mg FPD (Cohort 3) on Part B – Stratified by Sex		
14.4.9	Plasma Pharmacokinetic Parameters of PK10571 after Single Dose Administrations of FPD (Cohort 1), FPD (Cohort 2), FPD (Cohort 3), FPD (Cohort 4), and FPD (Cohort 5) Part A		
14.4.10	Plasma Pharmacokinetic Parameters of PK10571 after Single Dose Administrations of FPD (Cohort 1), FPD (Cohort 2), FPD (Cohort 3), FPD (Cohort 4), and FPD (Cohort 5) Part A – Stratified by Sex		
14.4.11	Plasma Pharmacokinetic Parameters of PK10571 after Administrations of xx mg FPD (Cohort 1), xx mg FPD (Cohort 2), and xx mg FPD (Cohort 3) on Day 1 Part B		
14.4.12	Plasma Pharmacokinetic Parameters of PK10571 after Administrations of xx mg FPD (Cohort 1), xx		

Table Number	Table Title	Validation Method	Shell Number (if repeat)
	mg FPD (Cohort 2), and xx mg FPD (Cohort 3) on Day 1 Part B – Stratified by Sex		
14.4.13	Plasma Pharmacokinetic Parameters of PK10571 after of xx mg FPD (Cohort 1), xx mg FPD (Cohort 2), and xx mg FPD (Cohort 3) on Day 7 Part B		
14.4.14	Plasma Pharmacokinetic Parameters of PK10571 after Administrations of xx mg FPD (Cohort 1), xx mg FPD (Cohort 2), and xx mg FPD (Cohort 3) on Day 7 Part B – Stratified by Sex		
14.4.15	Statistical Analysis of the Natural Log-Transformed Systemic Exposure of PK10571 Comparing xx mg FPD on Day 7 vs. xx mg FPD on Day 1 (Cohort 1)		
14.4.16	Statistical Analysis of the Natural Log-Transformed Systemic Exposure of PK10571 Comparing xx mg FPD on Day 7 vs. xx mg FPD on Day 1 (Cohort 2)		
14.4.17	Statistical Analysis of the Natural Log-Transformed Systemic Exposure of PK10571 Comparing xx mg FPD on Day 7 vs. xx mg FPD on Day 1 (Cohort 3)		
14.4.18	Dose Proportionality Assessment of PK10571 (Part A)		
14.4.19	Dose Proportionality Assessment of PK10571 for Day 1 and Day 7 (Part B)		

Note: Buffy coat analysis is exploratory and may not be undertaken; in such case, the tables will be blank with the note analysis no longer required.

Figure Number	Figure Title	Validation Method	Shell Number (if repeat)
14.4.1	Mean Plasma PK10571 Concentration-time Data after Single Dose Administrations of FPD (Cohort 1), FPD (Cohort 2), FPD (Cohort 3), FPD (Cohort 4), and FPD (Cohort 5) (Part A) on Linear and Semilogarithmic Scales		(a.s.year)
14.4.2	Mean Plasma PK10571 Concentration-time Data after Administrations of xx mg FPD (Cohort 1), xx mg FPD (Cohort 2), and xx mg FPD (Cohort 3) on Day 1 (Part B) on Linear and Semi-logarithmic Scales		
14.4.3	Mean Plasma PK10571 Concentration-time Data after Administrations of xx mg FPD (Cohort 1), xx mg FPD (Cohort 2), and xx mg FPD (Cohort 3) on Day 7 (Part B) on Linear and Semi-logarithmic Scales		
14.4.4	Mean Plasma PK10571 Concentration-time Data after Single Dose Administrations of FPD (Cohort 1), FPD (Cohort 2), FPD (Cohort 3), FPD (Cohort 4), FPD (Cohort 5) (Part A) Males vs. Females on Linear and Semi-logarithmic Scales		
14.4.5	Mean Plasma PK10571 Concentration-time Data after Administrations of xx mg FPD (Cohort 1), xx mg FPD (Cohort 2), and xx mg FPD (Cohort 3) on Day 1 (Part B) Males vs. Females on Linear and Semi-logarithmic Scales		
14.4.6	Mean Plasma PK10571 Concentration-time Data after Administrations of xx mg FPD (Cohort 1), xx mg FPD (Cohort 2), and xx mg FPD (Cohort 3) on Day 7 (Part B) Males vs. Females on Linear and Semi-logarithmic Scales		
14.4.7	Mean Plasma PK10571 Concentration-time Data after Administrations of xx mg FPD (Cohort 1) on Day 1 and Day 7 (Part B) on Linear and Semilogarithmic Scales		

Figure Number	Figure Title	Validation Method	Shell Number (if repeat)
14.4.8	Mean Plasma PK10571 Concentration-time Data after Administration of xx mg FPD (Cohort 2) on Day 1 and Day 7 (Part B) on Linear and Semilogarithmic Scales		
14.4.9	Mean Plasma PK10571 Concentration-time Data after Administration of xx mg FPD (Cohort 3) on Day 1 and Day 7 (Part B) on Linear and Semilogarithmic Scales		
14.4.10	Plasma PK10571 Concentration-time Profiles for All Subjects after Single Dose Administrations of FPD (Cohort 1), FPD (Cohort 2), FPD (Cohort 3), FPD (Cohort 4), and FPD (Cohort 5) (Part A) on Linear and Semi-logarithmic Scales	×	
14.4.11	Plasma PK10571 Concentration-time Profiles for All Subjects after Administrations of xx mg FPD (Cohort 1), xx mg FPD (Cohort 2), and xx mg FPD (Cohort 3) on Day 1 (Part B) on Linear and Semilogarithmic Scales		
14.4.12	Plasma PK10571 Concentration-time Profiles for All Subjects after Administrations of xx mg FPD (Cohort 1), xx mg FPD (Cohort 2) and xx mg FPD (Cohort 3) on Day 7 (Part B) on Linear and Semilogarithmic Scales		
14.4.13	Plasma PK10571 Concentration-time Data for Individual Subjects after xx mg FPD (Cohort 1), on Day 1 and Day 7 (Part B) on Linear and Semilogarithmic Scales		
14.4.14	Plasma PK10571 Concentration-time Data for Individual Subjects after xx mg FPD (Cohort 2), on Day 1 and Day 7 (Part B) on Linear and Semilogarithmic Scales		
14.4.15	Plasma PK10571 Concentration-time Data for Individual Subjects after xx mg FPD (Cohort 3), on Day 1 and Day 7 (Part B) on Linear and Semilogarithmic Scales		

Figure Number	Figure Title	Validation Method	Shell Number (if repeat)
14.4.16	Plasma Concentration-Time Profiles for PK10571 with Linear Regression for Estimating the Terminal Elimination Rate		
14.4.17	Scatter Plot for PK Parameters Vs Baseline FEV1 by Cohort (SAD)		
14.4.18	Scatter Plot for Vs PK Parameters Baseline FVC by Cohort (SAD)		
14.4.19	Scatter Plot for PK Parameters Vs Body Size by Cohort (SAD)		
14.4.20	Scatter Plot for PK Parameters Vs Gender by Cohort (SAD)		
14.4.21	Scatter Plot for PK Parameters Vs Baseline FEV1 by Cohort (MAD)	21	
14.4.22	Scatter Plot for PK Parameters Vs Baseline FVC by Cohort (MAD)		
14.4.23	Scatter Plot for PK Parameters Vs Body Size by Cohort (MAD)		
14.4.24	Scatter Plot for PK Parameters Vs Gender by Cohort (MAD)		

Listing Number	Listing Title	Validation Method	Shell Number (if repeat)
16.2	Subject Data Listings		
16.2.1	Discontinued Subjects		
16.2.1.1	Subject Disposition – Randomized Subjects	IP	
16.2.2	Protocol Deviations		
16.2.2.1	Protocol Deviations – Safety Population	IP	
16.2.3	Subjects Excluded from the Efficacy Analyses		
16.2.3.1	Analysis Populations –Safety Population	IP	
16.2.4	Demographic Data		
16.2.4.1	Demographic Data – Safety Population	IP	
16.2.4.2	Previous Medical History – Safety Population	IP	
16.2.4.3	Ongoing Medical History – Safety Population	IP	
16.2.4.4	Social History – Safety Population	IP	
16.2.5	Compliance and/or Drug Concentration Data		
16.2.5.1	PK Sampling Times – Safety Population	IP	
16.2.5.2	Dose Exposure – Safety Population	IP	
16.2.6	Individual Efficacy Response Data		
16.2.6.1	PK10571 Plasma Concentration-Time Data Listing by Subject (Part A)		
16.2.6.2	PK10571 Plasma Concentration-Time Data Listing by Subject (Part B)		
16.2.6.3	Plasma Terminal Elimination Rate of PK10571 for Individual Subjects after Single Dose Administrations of FPD (Cohort 1), FPD (Cohort 2), FPD (Cohort 3), FPD (Cohort 4), and FPD (Cohort 5) (Part A)		
16.2.6.4	Plasma Terminal Elimination Rate of PK10571 for Individual Subjects after xx mg FPD (Cohort 1) on Days 1 and 7 (Part B)		
16.2.6.5	Plasma Terminal Elimination Rate of PK10571 for Individual Subjects after xx mg FPD (Cohort 2) on Days 1 and 7 (Part B)		
16.2.6.6	Plasma Terminal Elimination Rate of PK10571 for Individual Subjects after xx mg FPD (Cohort 3) on Days 1 and 7 (Part B)		
16.2.6.7	PK Output text		

Listing Number	Listing Title	Validation Method	Shell Number (if repeat)
16.2.6.8	SAS Output for Part B Day 7 vs Day 1		(======================================
	Comparison (Cohort 1)		
16.2.6.9	SAS Output for Part B Day 7 vs Day 1		
	Comparison (Cohort 2)		
16.2.6.10	SAS Output for Part B Day 7 vs Day 1		
	Comparison (Cohort 3)		
16.2.6.11	SAS Output-Dose Proportionality Assessment		
	Part A		
16.2.6.12	SAS Output-Dose Proportionality Assessment		
	Part B Day 1		
16.2.6.13	SAS Output-Dose Proportionality Assessment		
	Part B Day 7		
16.2.7	Adverse Event Listings		
16.2.7.1	Adverse Event Data – Safety Population	IP	
16.2.8	Individual Laboratory Measurements and		
	Other Safety		
16.2.8.1	Hematology Data – Safety Population	IP	
16.2.8.2	Serum Chemistry Data – Safety Population	IP	
16.2.8.3	Urinalysis Data – Safety Population	IP	
16.2.8.4	Urine Drug, Cotinine and Alcohol Screen –	IP	
30	Safety Population		
16.2.8.5	Serology, PPD and TSH Data – Safety Population	IP	
16.2.8.6	Pregnancy Test and FSH Data – Safety	IP	
	Population		
16.2.8.7	Buffy Coat and Platelet Aggregation Data –	IP	
	Safety Population		
16.2.8.8	Physical Examination Data – Safety Population	IP	
16.2.8.9	Vital Signs Data – Safety Population	IP	
16.2.8.10	ECG Data – Safety Population	IP	
16.2.8.11	Chest X-ray – Safety Population	IP	
16.2.8.12	Prior and Concomitant Medications – Safety	IP	
	Population		
16.2.8.13	Pulmonary Function Data- Safety Population	IP	
16.2.8.14	SAS Mean Difference Output	IP	

Page 39 of 39 Confidential

Signature:

Email: [contact]
